Standard-of-care. At the time of this study, much like other contemporary NICUs, parents were allowed to be present in the NICU 24 hours per day, with significant variability in the amount, types and timing of actual parent engagement. Infant holding was supported, provided the infant could maintain physiological and temperature stability. Infants were held while on mechanical ventilation, but holding was not encouraged when infants were on oscillatory ventilation and/or when chest tubes were in place. Nurses and therapists fostered parent participation through instruction on caregiving and developmentally appropriate interactions, but these were balanced with other priorities of medical care. No specific amount of positive sensory exposures was targeted, and practices varied based on the comfort level of nurses, the medical team, and the parents. Suboptimal parent presence, holding, and language exposure have previously been reported at the study site. The study site is consistent with other hospitals, where there is significant variation in use of sensory based interventions and decreased parental involvement. The SENSE program addresses the current lack of a national standard for positive sensory exposures and the resultant inconsistency of application of these exposures across hospitalization.

SENSE multisensory program. The SENSE program includes the provision of specific types and amounts of evidence-based tactile, auditory, visual, vestibular/kinesthetic, and olfactory interventions to be conducted by parents with their preterm infants, with a specific amount defined for each day of hospitalization (see Appendix 1). The program changes across PMA, and a sensory support team fills in the gaps when parents are not available. The education and parent guidance that is part of the SENSE program was overseen by a neonatal therapist (with the study using a neonatal occupational therapist and physical therapist).

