Treatment fidelity/documenting sensory exposures. To assess treatment fidelity and to ensure treatment differentiation, sensory exposures (conducted by parents, the medical team, or the sensory support team) were captured on bedside logs for both groups. To ensure *treatment integrity*, we measured whether the daily doses defined in the SENSE program were being met each day, with specific attention to auditory and tactile exposures, which have large dose targets and are measurable by amount of time. Continuous review of sensory exposures during the course of the study also enabled activation of the sensory support team as needed. Differences in sensory exposure in the SENSE and standard-of-care groups are reported in a previous publication.

Masking participants and blinding evaluators. Parents were enrolled in this study, understanding that they would be assigned to one of two types of sensory approaches. They were masked from whether they were in the treatment group (SENSE program) or control group (standard-of-care), and the details of what we wanted them to do (within their assigned approach) were not communicated until after enrollment. All assessments in the NICU were conducted at the infant's bedside by a certified and trained evaluator, who was blinded to treatment assignment (as well as study details).

Medical factors. Medical factors were collected from both groups using the EPIC electronic medical record to define the characteristics of the sample and enable statistical control of other factors that can impact outcome. From these factors, a medical risk score was defined as the infant having any of these factors during the NICU hospitalization: inotropic support, patent ductus arteriosus (PDA), necrotizing enterocolitis (NEC), parenteral nutrition > 21 days, mechanical ventilation > 7 days, bronchopulmonary dysplasia, or cerebral injury (grade III or IV intraventricular hemorrhage or cystic leukomalacia) due to evidence associating them with adverse neurodevelopmental outcome .

Social factors. Social factors were collected from EPIC as well as from the parent questionnaire. A social risk score, used in parallel research studies and modified for this study, was used to assess family environment after NICU discharge.

Outcomes at term equivalent age, prior to NICU discharge.

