First, mixed random effects models were used to investigate group differences in NNNS, ASQ, and other outcomes. Correlation between siblings, who are multiples, were modeled by using mother-infant dyad as a random effect. PMA at the time of assessment was controlled for due to its previously reported relation to neurobehavioral outcome. To further explore group differences, a second analysis was conducted, controlling for baseline covariates of social risk score and medical risk score. In addition, a final analysis was conducted to understand the potential impact of parent-driven, compared to sensory support driven, sensory interventions. An interaction between parent engagement (50% of interventions done by the parents) and treatment group was investigated in a factorial model. Other analyses of outcomes included mixed effects repeated measures ANOVA for continuous measures across time and using logistic regression for categorical outcomes of measures conducted at one point in time. The threshold of significance was $p = 0.05$.

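### The second analysis calls the medical and social risk scores baseline covariates, but the medical score covers the whole NICU stay and the social score is probably collected partly after randomisation

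*Combined protocol and SAP*

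**What the plan says.** The Statistical analysis section sets out a first mixed model that adjusts for PMA at assessment, with the mother-infant dyad as a random effect. It continues: "To further explore group differences, a second analysis was conducted", "controlling for baseline covariates of social risk score and medical risk score".

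The two scores are defined earlier. Under Medical factors, "a medical risk score was defined as the infant having any of these factors during the NICU hospitalization"; the list includes "parenteral nutrition > 21 days, mechanical ventilation > 7 days". Under Social factors, "Social factors were collected from EPIC as well as from the parent questionnaire", and the score "was used to assess family environment after NICU discharge". No section gives a version of either score limited to data from before allocation.

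Overview of procedures places enrolment within 7 days of birth, with the allocation envelope opened after enrolment. It places the maternal questionnaire at 35-41 weeks PMA and at one year corrected age. The SENSE multisensory program section describes an intervention "with a specific amount defined for each day of hospitalization".

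**The concern.** A covariate fixed before allocation cannot be altered by treatment, so in a linear model adjusting for it leaves the target of estimation unchanged and may improve precision. A covariate that accrues while treatment is being given carries no such guarantee. If SENSE changes the score, and the score affects the outcome or shares unmeasured causes with it (illness severity is the obvious candidate), the adjusted group difference is no longer the total effect of being randomised to SENSE.

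A reader told that the second model is baseline-adjusted will take it as another estimate of the same effect as the first. If the two differ, the cause could be chance, ordinary covariate adjustment, or conditioning on a consequence of treatment, and the label hides the third possibility.

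**Working it through.** The plan gives no figure on this point to reproduce. The check has two parts: the plan's own timings, then an illustration of size with assumed inputs.

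**Timing of the medical score**

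- Latest enrolment: day 7 of life. Allocation follows enrolment.
- Parenteral nutrition beyond 21 days cannot be established until at least 21 − 7 = 14 days after that limit.
- Ventilation beyond 7 days cannot be complete by day 7.
- The gap between enrolment and opening the envelope is not stated. SENSE parents received verbal education within one week of enrolment, so allocation was known by about day 7 + 7 = 14. The 21-day criterion still falls after it.
- The other components (inotropes, PDA, NEC, bronchopulmonary dysplasia, cerebral injury) may fall before or after allocation. The score therefore mixes the two periods, and SENSE is delivered during the later one.

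**Timing of the social score**

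- Birth at 32 weeks or earlier plus 7 days puts enrolment at no later than 33 weeks PMA, or 33 weeks 6 days if 32 weeks includes 32 weeks 6 days.
- The questionnaire starts at 35 weeks PMA, so any questionnaire item is recorded at least 8 days to 2 weeks after enrolment.
- The score's stated purpose concerns the period after discharge, yet the first outcome block is headed "Outcomes at term equivalent age, prior to NICU discharge".
- The items are not listed. Some may be stable traits that are merely recorded late.

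**Illustration of size (all inputs assumed)**

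Simulation with n = 4,000,000. Severity U, the errors e0 and e1, and the outcome noise are standard normal; A is randomised 1:1.

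- M0 = 1[U + e0 > c0]: flag already fixed before allocation, in 0% or 25% of infants.
- M = M0 or 1[U + e1 − shift × A > c1], with c1 set so that 50% of controls are flagged; shift 0, 0.25 or 0.5.
- Outcome = bU × U + g × M + noise, with bU 0, 0.5 or 1 and g 0 or 0.5. Higher values are worse.

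The result is the coefficient of A adjusted for M minus the unadjusted coefficient, in control-arm outcome SDs. The ranges exclude bU = g = 0.

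| Flag fixed before allocation | Flag rate, control to SENSE | Adjusted minus unadjusted |
|---|---|---|
| 0% | 50% to 43.0% | 0.034 to 0.075 SD |
| 0% | 50% to 36.2% | 0.067 to 0.148 SD |
| 25% | 50% to 45.0% | 0.024 to 0.056 SD |
| 25% | 50% to 40.7% | 0.045 to 0.105 SD |

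With shift = 0 the difference is 0 to rounding (at most 0.001), and with bU = g = 0 it is 0 at every shift. A constant treatment effect adds equally to both estimates and cancels. A positive difference here shrinks an apparent benefit; the sign reverses if SENSE raises the score.

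Scale, from the Power section:

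- Planned differences: 2.2/2.4 = 0.917 SD (NNNS Excitability) and 9.5/11.1 = 0.856 SD (ASQ Communication), using the normative SDs.
- Smallest non-zero shift: 0.024/0.917 = 3%. Largest: 0.148/0.856 = 17%.
- Standard error at 23 per arm: √(2/23) = 0.295 SD, so the largest shift is 0.148/0.295 = 0.50 SE. At the planned n = 60 at term (30 per arm), √(2/30) = 0.258 SD and the ratio is 0.57.

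These are maxima over the chosen grid, not bounds. With g = 1 the largest shift is about 0.18 SD. A second model, on the NNNS scale, assumes a total effect of −2.2, 60% of controls flagged, a flag worth 1.5 points and residual SD 2. If SENSE lowers the flag rate by 5, 10 or 20 percentage points, the adjusted effect is −2.12, −2.05 or −1.90 without shared frailty. With frailty worth 1 point per SD it is −2.04, −1.89 or −1.58. The extreme case loses 2.20 − 1.58 = 0.62 points, or 0.62/2.2 = 28%. With no change in the flag rate the adjusted effect stays at −2.20.

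**The case against.** The best defence is that little rests on this model. It is introduced as exploratory, no power statement depends on it, and the first model does not name the scores. The document states the hospital-stay window openly, so a careful reader can see what the medical score is. Adjusting for prognosis is a legitimate exploratory aim. Nothing in the documents shows that SENSE changes any component of either score, and late recording of a fixed social trait causes no bias. The document is also dated 2021 and written in the past tense, so choosing new covariates now would be post hoc.

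Most of this stands, and it limits the weight of the point. Bias is possible, not shown. The social half is properly a request for clarification. The medical score reads as a yes/no flag, which does not affect the argument about its time window. One further caution: the covariate-selection rule in the Statistical analysis section lets imbalanced factors enter the model without saying which model, so the first model can be called unaffected only as it is described.

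What does not stand is that an open definition cures the label. The section that names the model calls the covariates baseline, and that tells readers how to interpret the estimate. The same selection rule leaves out factors already represented in the two scores, so the scores stand in for their components.

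**Conclusion.** The concern holds. For the medical score the label is wrong on the plan's own timings, with high confidence and no outside assumption. For the social score it is probably wrong in part, because that depends on items the documents do not list.

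The effect on the estimate cannot be determined from the documents, because they do not show whether SENSE changes either score. The main illustration gives a shift of 0 if it does not, and 0.02 to 0.15 SD if it lowers the flag rate from 50% to between 45% and 36%. Stronger assumptions give more, up to 28% of the planned NNNS difference in the most extreme case tried. This is a modest problem confined to the second analysis. It deserves correction because it changes what that analysis can be said to estimate.

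**What to change.** - Restrict the second model to variables fixed before allocation. Begin with gestational age at birth: its stratum is known for every randomised dyad and it is named in neither the first nor the second model. Add sex, multiple birth, and medical or social items known at enrolment, where recorded. If outcomes had already been seen when these were chosen, say that the choice was post hoc.
- State when each item of both scores is recorded.
- Report the whole-stay medical score and the post-discharge social score as descriptors or outcomes.
- If the scores stay in the model, label it as adjusted for post-randomisation variables and do not present it as a baseline-adjusted estimate of the SENSE effect.

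The cost is a wording change and one re-specified secondary model. The documents do not say whether pre-allocation medical status or enrolment-time social items were abstracted, so this must be checked. If they were not, use gestational age alone or only relabel; relabelling needs no new data. Enrolment-time covariates may explain slightly less outcome variance than the whole-stay score, at a small loss of precision.

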SENSE program education. Parents randomized to the SENSE group received an educational booklet for the SENSE program which informed them about the premise of the multisensory interventions, along with identified targets in the amounts of daily multisensory exposures that are tailored to each infant's PMA. Parents could choose to provide one sensory exposure at a time or could provide multisensory interventions, based on the infant's tolerance. Parents were able to choose different types of each sensory exposure from options that have evidence to support their use and are appropriate at each PMA. The parents and medical team also opted for exposures within an infant's range of tolerance (such as using gentle human touch for an infant too sick to be transferred out of the bed to be held). Parents also received verbal education by the neonatal therapist on the research team within one week of enrollment and at least weekly thereafter to reinforce content in the booklet.

The sensory support team. When the parents or family members were unable to reach the target doses as defined in the SENSE program, a member of the sensory support team was assigned to deliver appropriate multisensory interventions. The sensory support team consisted of trained volunteers who provided gentle human touch and language exposure to medically stable infants as directed by the research team.

Modifications to the sensory intervention based on infant factors. The SENSE program is tailored to be responsive to each infant's cues when receiving the stimuli as

well as individualized based on concurrent medical issues. The neonatal therapist on the study team assessed the infant's tolerance each week, or more often if needed, and adjusted the multisensory interventions accordingly when not tolerated. The infant assessment used for the SENSE program is part of the manualized intervention and consists of infant observations, evaluation, and collaboration with the medical team. Any modifications to the structured dose and timing of the multisensory interventions were communicated to the parents, medical team, and sensory support team and documented by the research team.

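### The final factorial model splits both arms on a post-randomisation parent share that assignment itself changes, so its within-cell and engagement-adjusted treatment contrasts are not effects of SENSE

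*Combined protocol and SAP*

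**What the plan says.** The *Statistical analysis* section lists three steps: a mixed-model comparison of the groups, the same comparison adjusted for social and medical risk scores, and a final analysis meant to "understand the potential impact of parent-driven, compared to sensory support driven, sensory interventions". For that last step, "An interaction between parent engagement (50% of interventions done by the parents) and treatment group was investigated in a factorial model". Crossing the factor with treatment means that infants in both arms must be classified.

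The data source is common to the arms. Under *Treatment fidelity/documenting sensory exposures*, "sensory exposures (conducted by parents, the medical team, or the sensory support team) were captured on bedside logs for both groups".

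The delivery of exposures differs by arm:
- *SENSE multisensory program*: "a sensory support team fills in the gaps when parents are not available".
- *The sensory support team*: this team is called on "When the parents or family members were unable to reach the target doses as defined in the SENSE program". It consists of "trained volunteers who provided gentle human touch and language exposure to medically stable infants".
- *Standard-of-care*: "No specific amount of positive sensory exposures was targeted". No support team is described there.
- *Overview of procedures*: SENSE parents also receive education and a therapist's daily support to take part.

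The plan does not define the denominator of the 50% share (all logged exposures or the target dose), its unit (minutes or counts) or its period. It gives no separate rule for standard care.

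**The concern.** A subgroup factor supports a randomised comparison within its levels only if assignment cannot move infants between levels. Here assignment can move them in two ways. The top-up lowers the parents' share in SENSE for a given amount of parent time. Education and daily support may raise parent time, and so the share. Neither applies in standard care as described.

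The engaged SENSE infants and the engaged control infants may then come from different kinds of family, and so may the two less engaged groups. If families who are more present have infants with different outcomes, the treatment contrast within each cell mixes any effect of SENSE with that difference. The *Power* section itself links poor parent engagement, in low-stimulation settings, to poorer language outcomes, but gives no strength. At stake is whether a result such as a benefit seen among engaged families could be read as an effect of the programme.

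**Working it through.** The plan states no figure for this analysis. Its power calculation (46 in total, 23 per group) concerns the primary comparisons and does not bear on this point.

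**Inputs.** The factor, the SENSE-only top-up, the absence of a target in standard care and the parent support in SENSE come from the sections cited above. Hours, prognostic strength and any SENSE effect on parent time are not given. The dose targets are referred to Appendix 1, which is not in the text available to me. All numerical inputs below are therefore assumptions.

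**Share by arm.** Let P be parent time, M other caregivers' time and T the target. If the share is taken over all logged exposure and the gap is fully filled:
- standard care: P/(P+M)
- SENSE: P/max(P+M, T)

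**Single families (hours per day).**
- P = 1, M = 0.5, T = 3: standard care 1/1.5 = 67%; SENSE 1/3 = 33%. The family drops to the lower cell in SENSE.
- The same family, with SENSE doubling P: 2/max(2.5, 3) = 67%. The shift is undone.
- P = 0.6, M = 0.8, T = 2: standard care 0.6/1.4 = 43%; SENSE with P doubled 1.2/max(2.0, 2) = 60%. The family moves up.

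**Simulation, zero treatment effect.** 400,000 infants per scenario; P lognormal (median 1 h, log-SD 0.8); M lognormal (median 0.5 h, log-SD 0.5); T = 2 to 4 h; outcome correlated 0.2 to 0.4 with underlying parent time. Differences are SENSE minus control in SD units; positive favours SENSE.

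| Parent time in SENSE | Target | Gap filled | Engaged cell | Other cell |
|---|---|---|---|---|
| unchanged | 2-4 h | all | +0.09 to +0.43 | +0.06 to +0.31 |
| unchanged | 3 h | half (correlation 0.4) | +0.24 | +0.18 |
| doubled | 3 h | all | +0.05 to +0.10 | +0.02 to +0.03 |
| doubled | 3 h | half (correlation 0.4) | +0.04 | -0.05 |
| doubled | 2 h | all | 0.00 to +0.01 | -0.06 to -0.11 |

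In the first row, 77% of controls count as engaged, against 49%, 31% and 19% of SENSE infants at targets of 2, 3 and 4 h. The interaction is shifted by only 0.02 to 0.12 SD.

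**Second set of assumptions.** Target 100 units; median parent amount 45 (log-SD 0.7); median other amount 10 to 45 (log-SD 0.5); correlation 0, 0.3 or 0.5.
- With parent time unchanged, the engaged fraction falls from 96% to 44% (other amount 10) or from 50% to 37% (other amount 45), so 13% to 52% of families change cell.
- At correlation 0.3 the lower cell shows +0.02 to +0.31 SD and the upper +0.10 to +0.25 SD. At correlation 0 there is no bias.
- With parent time doubled, correlation 0.5 and other amount 30, the cells show -0.22 and -0.03 SD.
- The overall randomised difference stays about 0 throughout.

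**Type I error at n = 60**, the number planned at term age. With parent time unchanged and correlation 0.3 to 0.5, the treatment test adjusted for the split rejects in 6% to 31% of trials. The 31% comes from the scenario with 96% of controls in the upper cell; with other amounts of 20 and 30 the range is 6% to 19%. With parent time doubled it is about 5% to 9%. The interaction test is at about 4% to 7% in every scenario. That reflects noise more than absence of bias: with four cells of 15, its standard error is √(4/15) = 0.52 SD, so a shift of 0.12 SD is 0.12/0.52 = 0.23 standard errors.

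**Would a common denominator repair it?** With the same absolute parent-time cut in both arms, the spurious differences are at most 0.01 SD if SENSE leaves parent time unchanged, but -0.10 to -0.35 SD in both cells if SENSE raises it by 50% to 100%. A split on engagement that assignment cannot affect gives about 0 in every scenario.

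**The case against.** The strongest reply is that this analysis comes last, is exploratory, and names an interaction test that stayed close to nominal. The plan does not say that cell-specific effects will be reported as SENSE effects. This stands as a limit on severity. It does not settle the matter, because a factorial model on parent-driven versus support-driven delivery invites a reading of the treatment difference within each cell.

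A reader might go further and infer that the split must produce a consistent false benefit of SENSE in both cells. The documents do not support that. SENSE is meant to increase parents' participation, and the size of that increase is not stated; a large enough increase offsets or reverses the effect of the top-up. The support team gave only touch and language exposure, and only to medically stable infants, so the gap may be filled in part. The denominator is also undefined, so the formula for the share is one reasonable reading.

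These points remove any claim about direction. They do not make the cells comparable, and an unknown sign is itself a reason not to interpret the contrasts.

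**Conclusion.** The concern holds for the within-cell and engagement-adjusted treatment contrasts of the final factorial model. They lose the protection of randomisation because assignment acts on both parts of the share, and they are biased if engagement is prognostic. Under the hour-based assumptions, the spurious difference is about +0.06 to +0.43 SD in both cells with unchanged parent time and full top-up; otherwise it shrinks, vanishes or reverses, for example to about 0 and -0.11 SD. These sizes are illustrations, since hours, top-up and prognostic strength are all assumed.

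Nor should a reader infer that the trial's main result is compromised. The first randomised comparison does not use the split and is unaffected, and the interaction test was only slightly disturbed in these simulations.

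**What to change.** - Label the observed 50% split descriptive and non-randomised. Do not report its cell-specific or engagement-adjusted treatment contrasts as effects of SENSE.
- State the numerator, denominator, unit and period of the parent share.
- Address parent-driven versus support-driven delivery within the SENSE arm only, where both sources exist. Present it as an observational association adjusted for EGA stratum and the social and medical risk scores, keeping the planned control for PMA at assessment and the random effect for siblings.
- Optionally, add a treatment-by-predicted-engagement model as a sensitivity analysis. Its predictors must be fixed before randomisation and its predictions cross-fitted. It should not replace the analysis above. It would be fitted in roughly 30 to 35 SENSE infants, the documents do not show which social items were recorded before randomisation (the questionnaire that supplies some was completed at 35-41 weeks PMA), and it does not measure who delivered the exposures.

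The labelling costs almost nothing, and the SENSE-arm model uses data already logged. The price is that the delivery question is answered only as an association, open to residual confounding. It also rests on about half the sample (on equal allocation, 60/2 = 30 infants at term age and 48/2 = 24 at one year), with a wider interval.

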Questionnaire (ASQ) Communication score. This was chosen as our primary outcome of interest, due to previous findings of poorer language outcomes in preterm infants hospitalized in low stimulation environments with poor parent engagement. The variance of the Communication score was estimated using a sample of preterm infants enrolled in our lab in 2011 who received the ASQ at age 3 years. A sample of $n=46$ provides 80% power when the true group mean ASQ difference is 9.5 (2-sided test with $\alpha=0.05$). In a normative sample, the Communication score on the ASQ has a mean of 52.9 with a standard deviation of 11.1. A total sample of $n=46$ (23 in each group) would be a large enough sample to detect a difference of less than 1 standard deviation across groups at the one-year follow-up assessment. Seventy infants were enrolled to account for 15% attrition during the course of the NICU hospitalization (for $n=60$ at term age) and another 20% attrition by the one-year follow-up assessment ($n=48$ at one-year of age).

Overview of procedures. Parent-infant dyads, enrolled within 7 days of birth, were randomized to either the standard-of-care group or SENSE multisensory program group. The randomization scheme was stratified on level of immaturity (≤ 28 weeks EGA or > 28 weeks EGA) and was uploaded to REDCap prior to study initiation. The biostatistician, who was not involved in other study procedures, established the randomization allocation sequence. Various members of the research team (research coordinator, principal investigator, neonatal therapist) enrolled families, pulling a sealed envelope that disclosed the group assignment after enrollment. Parents with infants in the SENSE group were provided with SENSE program education and daily support by a neonatal therapist to engage in the SENSE program (described below) in addition to receiving standard-of-care. Sensory exposures were tracked on bedside logs that contained sensory exposure dose targets for each day. The monitored standard-of-care

group received standard NICU care at the study site (described below) and tracked sensory exposures on bedside logs.

Standardized measures of maternal mental health and infant development were contained in a questionnaire that was completed by mothers at 35-41 weeks PMA in the NICU and at one-year corrected age. The questionnaire has been used in our longitudinal studies of preterm infants since 2007 and takes approximately 30 minutes to complete.

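### The exploratory parent-engagement interaction uses a 50% cut where the parent-delivered share could be kept continuous; the test is weak either way, so a null result is uninformative

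*Combined protocol and SAP*

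**What the plan says.** The Statistical analysis section ends its main sequence with an analysis of who delivers the intervention: "a final analysis was conducted to understand the potential impact of parent-driven, compared to sensory support driven, sensory interventions". The model is given in one sentence: "An interaction between parent engagement (50% of interventions done by the parents) and treatment group was investigated in a factorial model". The only definition of the factor is "parent engagement (50% of interventions done by the parents"). Nothing more is specified. The plan gives no reason for 50%. It does not say whether interventions are counted or timed, whether exposures given by the medical team belong in the denominator, or on which side exactly 50% falls. It has no continuous or sensitivity version and no power statement for this test.

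The section on treatment fidelity describes the data: "sensory exposures (conducted by parents, the medical team, or the sensory support team) were captured on bedside logs for both groups". It singles out "auditory and tactile exposures, which have large dose targets and are measurable by amount of time".

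The sensory support team paragraph says that this team steps in when families do not reach the SENSE targets. The Power section enrols 70 and expects 60 infants at term age and 48 at one year. Its power statements concern the two group comparisons only.

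**The concern.** A single threshold inside a factorial model is most naturally a two-level factor. On that reading an infant at 51% and one at 95% count as the same, while infants at 49% and 51% count as opposites. The 50% indicator cannot be built without first computing the share, so the detail is in hand and is then dropped.

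This is the only analysis in the plan aimed at parent-driven versus support-driven delivery. It relies on an interaction in a sample sized for a main effect. A non-significant result could easily be read as showing that it does not matter who delivers the programme, and the plan gives no caution against that.

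**Working it through.** **Inputs from the plan.** 70 enrolled; 15% then 20% attrition; 60 and 48 expected; target differences 2.2 (NNNS Excitability) and 9.5 (ASQ Communication); printed reference SDs 2.4 and 11.1; two-sided alpha 0.05.

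**The plan's sample figures reproduce.** 70 × 0.85 = 59.5, stated as 60. Then 59.5 × 0.80 = 47.6, stated as 48.

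**Information kept after a cut.** If the outcome is linear in the share X, the fraction kept is the squared correlation between X and the indicator X ≥ c. With a proportion p above the cut:
- normal X: φ(z_p)² / [p(1 − p)], which is 2/π = 0.637 at p = 0.5;
- uniform X: 3p(1 − p), which is 0.75 at p = 0.5;
- beta-distributed X cut at 0.5: computed exactly.

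The plan gives no distribution for the share, so every row below is an assumption.

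| Assumed share | Above / below 50% | Information lost | 60 act like | 48 act like |
|---|---|---|---|---|
| Normal | 50/50 | 36% | 38 | 31 |
| Normal | 80/20 | 51% | 29 | 24 |
| Normal | 90/10 | 66% | 21 | 16 |
| Bell-shaped, Beta(5,5) | 50/50 | 33% | 40 | 32 |
| Uniform | 50/50 | 25% | 45 | 36 |
| U-shaped, Beta(0.5,0.5) | 50/50 | 19% | 49 | 39 |
| U-shaped, Beta(0.3,0.3) | 50/50 | 14% | 51 | 41 |
| Skewed, Beta(4,2) | 81/19 | 44% | 34 | 27 |

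**Power by simulation.** Ordinary least squares with arm, engagement and their product; residual SD 1; the same share distribution in both arms; outcome linear in the share in the SENSE arm only, at an assumed slope of 0.8 SD per SD of share.

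| Assumed share | n=60, continuous / cut | n=48, continuous / cut |
|---|---|---|
| Normal, 50/50 | 82% / 63% | 73% / 52% |
| Normal, 80/20 | 83% / 46% | 73% / 38% |
| Uniform | 84% / 70% | 75% / 60% |
| U-shaped, Beta(0.5,0.5) | 83% / 72% | 73% / 62% |

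Sibling clustering and adjustment for PMA are left out, so these powers are illustrative.

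**Smallest detectable 2x2 interaction.** SE = SD × √(sum of 1/cell n). For 80% power, multiply by 1.96 + 0.84 = 2.80.
- n=60, four cells of 15: 2.80 × √(4/15) = 1.45 SD.
- n=48, four cells of 12: 2.80 × √(4/12) = 1.62 SD.
- n=60, 80/20 in each arm (24 and 6): 2.80 × √(2/24 + 2/6) = 1.81 SD.
- n=48, 80/20 in each arm (19.2 and 4.8): 2.80 × √(2/19.2 + 2/4.8) = 2.02 SD.

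On the printed reference SDs, the differences the trial was sized for are 2.2/2.4 = 0.92 SD and 9.5/11.1 = 0.86 SD. With even cells the interaction would have to be 1.45/0.92 = 1.6 times the target difference at term age, and 1.62/0.86 = 1.9 times at one year.

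**The continuous version is also limited.** With a standardised share and n/2 infants per arm, the SE of the slope difference is √(4/n). The detectable slope is 2.80 × √(4/60) = 0.72 SD per SD of share at n=60 and 2.80 × √(4/48) = 0.81 at n=48. Keeping the share continuous recovers precision but does not make this a well-powered test.

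**The case against.** Three stronger readings are tempting, and the documents do not support them.

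- A reader might infer that the cut always discards at least a third of the information. That needs a roughly normal or off-centre share and a linear effect. The plan states neither, and a flat or U-shaped share loses about 15-25%.
- A reader might infer that most of the test's power goes. Among the simulated cases only one, an 80/20 split at n=48, loses close to half (73% to 38%). The others lose between about a seventh and under a half.
- A reader might take the logs as a complete, timed record. The plan says that exposures were captured by deliverer. It calls only auditory and tactile exposures measurable by time and says nothing about completeness.

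The best case for the cut is that a majority rule is a natural meaning of parent-driven delivery and is less exposed to logging error. If the true effect is a step at 50%, the ranking reverses: for a 1.5 SD step with a Beta(4,4) share, power is about 80% cut against 60% continuous at n=60, and 70% against 49% at n=48. The 0.8 slope is also large and has no source in the plan. At 0.4, with the same share, power is 31% against 24% (n=60) and 26% against 19% (n=48). Sample size is then the main limit, and a continuous term does not cure it.

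There is also a structural point that affects both versions. Engagement arises after randomisation, and SENSE is designed to change it. The support team is described only as filling gaps in SENSE targets, so non-parent delivery among controls is presumably by the medical team, and the share may mean something different in each arm. Cells may also be uneven: an assumed 15/15 in SENSE and 28/2 in control gives 2.80 × √(2/15 + 1/28 + 1/2) = 2.3 SD.

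All of this stands as a limit on interpretation. It does not favour an unexplained cut over the share itself, because the plan neither claims a step at 50% nor gives another reason for the threshold.

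**Conclusion.** The point holds, conditionally on the shape of the effect. Reading the factor as two-level is an inference from the threshold and the factorial model, but a strong one. Under a roughly linear effect the cut costs about 36% of the information for an evenly split normal share, about 15-25% for a flat or U-shaped share, and half or more when a normal share splits 80/20 or beyond. Under a true step at 50% it costs nothing. Whatever the shape, the planned 2x2 test reaches 80% power only for interactions of about 1.45 SD (n=60) or 1.62 SD (n=48) with even cells, and larger ones with uneven cells. A null result therefore cannot settle whether the deliverer matters. The defect is confined to this exploratory analysis; the primary group comparisons and their power statements do not depend on it.

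**What to change.** - Make the primary version of this exploratory analysis the parent-delivered share as a continuous term (for example per 10 percentage points) with its product with treatment, and check for curvature.
- Define the share: count or minutes, which exposures it covers, and whether medical-team delivery is in the denominator. State on which side exactly 50% falls.
- Keep the 50% split as a descriptive or sensitivity analysis, with cell sizes by arm.
- Report the interaction estimate with a 95% interval. Give SENSE contrasts only at share values observed in both arms.
- Label the results exploratory, because engagement arises after randomisation and non-parent delivery may differ by arm. State that non-significance is not evidence that the deliverer does not matter.

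The cost is small: the same data and the same model degrees of freedom, apart from the curvature check. The downsides are a linearity assumption, greater dependence on log quality, and the work of settling the denominator.
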